7.1 Drop-out

Participants may withdraw from the study at any time without giving a reason. Upon request, all samples collected up to that point will be destroyed and all stored data will be deleted.

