6.2 Data management

The REDCap database is used for digital data collection. Each study participant will be assigned a six-digit identification number (ID) for anonymization purposes. Personal data will only be stored in ID-encrypted form. The password-protected master list, which contains the assignment of IDs to personal data, ensures that personal data can be deleted when the study is completed. The master list is stored on a secure data server at the Paracelsus Medical University of Salzburg and is only accessible to the researcher responsible for recruitment, eligibility checks and allocation. Data from medical examinations and surveys are stored in spreadsheet files. Only authorized researchers have access to the data. Participants can access their personal data after completion of the study.

Written consent will be obtained from all study participants for the use of their personal data. The consent forms will include a specific clause on the protection of personal data, informing study participants of how their data will be handled and stored, the purpose of the research, the contact details of the data protection officer and their rights.

All personal data will be handled as defined in General Data Protection Regulation (EU 2016/679), and Finnish Data Protection Act 1050/2018.

Each person involved in the conduct of the study (hiking guides, assistants, etc.) will sign a confidentiality agreement before the start of the study, which will be countersigned by the principal investigator of the study. Confidentiality refers to all circumstances that become known through participation in the study, in particular information about study participants, employees and other cooperation partners regarding economic, operational, technical, tax and personal circumstances as well as internal matters of any kind.

The data will be used for scientific purposes and for possible publication in scientific journals and conferences. In addition, the results of the study will be used for the further development and implementation of effective, sustainable and cost-effective nature-based therapies (including health equity, nature conservation and health economics aspects).

Saliva samples from the Padua (NATURE-MET-P) and Barcelona (NATURE-MET-B) studies will be sent to the Paracelsus Medical University for analysis. The probes will only be labelled with an identification number (ID), so the analysis will be completely anonymous and experimenter-blinded.

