6.3 Statistics

All statistical analyses will be performed using the R-GNU software environment (General Public License, R Foundation for Statistical Computing, Vienna, Austria) and SPSS (IBM). Statistical significance will be set at the level of a < 0.05 for all tests. Randomly missing values will be replaced using the standard procedure, last outcome carried forward (LOCF). The statistical analysis will be carried out by a biometrician. The data will be blinded again in order to exclude a possible bias with regard to an expected result.

Statistical analyses will be performed in accordance with the intention-to-treat principles and reporting will adhere to the CONSORT-statement, including CONSORT flow chart (Calvert et al., 2013; CONSORT, 2019).

After a positive vote, the study will be preregistered in the ISRCTN registry (https://www.isrctn.com/).

Check for normal distribution

The Shapiro-Wilk test will be applied to check for normal-distribution. Depending on data distribution, parametric or non-parametric tests will be applied.

Analysis of Baseline values

To analyze possible baseline differences between the two groups, a t-test for unconnected samples is performed for normally distributed variables and a Mann-Whitney Utest for non-normally distributed parameters. Nominally scaled variables are analyzed using the chi-square test. If any baseline variables are significantly different between the groups, secondary analysis will be conducted including these variables to adjust for any residual confounding not prevented by the randomization.

Longitudinal Data analysis

Depending on data distribution, parametric or non-parametric tests will be applied. Participant data will be compared in terms of baseline data, including outcome variables as well as demographics (unpaired Student-T-Test or Wilcoxon-test).

For longitudinal data analysis, analyses of variance (ANOVA) or linear mixed models (LMM) are used for normally distributed data.

For non-normally distributed samples, a non-parametric analysis of variance (e.g. f1.LD.f1) is performed using the nparLD package (Noguchi et al., 2012).

Models will include random effects for temporal and spatial correlations and fixed effects for: (1) intervention group; (2) time effects characterizing changes between pre- and post-intervention; and (3) interaction between the intervention group and the pre- and

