post-intervention temporal effects, representing the group contrast. This determines whether or not the intervention has an effect. If any baseline variables are significantly different between the groups, secondary analysis will be conducted including these variables to adjust for any residual confounding not prevented by the randomization.

Multiple testing:

We will adjust for multiple testing, e.g., Benjamini-Hochberg or Holm-Bonferroni.

7 Methods: Data monitoring

The responsibility for the complete and correct data collection and documentation as well as the safe storage of the data in the context of the clinical study lies with the staff of the Paracelsus Medical University and the University Clinic for Internal Medicine I of the University Hospital Salzburg.

Data will only be shared with the RESONATE Lead Partner in an ID-encrypted form and in accordance with the RESONATE Data Management Plan (see chapter 6.2 Data management).

Data collection and storage is implemented in such a way as to minimize the possibility of inaccurate, erroneous and/or incomplete data entry. Entries and corrections can only be made by authorized persons. All entries and corrections are dated, documented and traceable or recoverable.

Internal audits shall be conducted at least three times: (1) prior to the start of the clinical trial, (2) during the conduct of the clinical trial and (3) after the completion of the clinical trial. The following activities are planned as part of the internal audits:

- Verification that the trial site meets the requirements of the clinical trial, e.g. requirements for the trial population, equipment, storage of trial materials.
- Comparison of source data
- Verification of proper and safe storage of samples

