7.2 Adverse events

Any unexpected or adverse events will be documented and promptly reported to the Ethics Committee.

8 Ethics and dissemination

Clinical trial results will be published in peer-reviewed journals and presented at scientific conferences. All publications and dissemination activities will respect the protection of personal data.

Publication rights are held by the parties involved in the study:

Lead partner:	Institute of Ecomedicine Paracelsus Medical University, Salzburg a.o. Univ. [name]. [name] and Team
Cooperation partner:	University Clinic for Internal Medicine I, with Gastro- enterology-Hepatology, Nephrology, Metabolism and Diabetology Salzburg University Hospital Prim. Univ. [name]. [name] and Team
RESONATE project partner	in accordance with the RESONATE Data Manage- ment Plan and the RESONATE Authorship Guide- lines RESONATE Lead Partner: Department of Cognition, Emotion, and Methods in Psychology University of Vienna [name], BSc MSc PhD and Team

Following FAIR Guiding Principles for scientific data management and stewardship, RESONATE will ensure that data generated and re-used throughout the project will be findable, accessible, interoperable, and reusable. As the primary repository, we will share and archive data on the Open Science Framework (https://osf.io/), which is a free and accessible platform.

To promote findability and implement our results within the wider nature-based solutions community, we will also share information and links to our results and datasets on OP-PLA (https://oppla.eu/), the EU repository for Nature-Based Solutions, to share and archive data. OPPLA is an open platform which can be accessed by people for different purposes, including non-scientific audiences. This will ensure that the results and benefits of the RESONATE project will also reach health care professionals, therapists, and municipalities. The master list, which combines ID and name, is deleted before the study data is published.

9 References

- Adams-Campbell, L. L., Taylor, T., Hicks, J., Lu, J., & Dash, C. (2021). The Effect of a 6-Month Exercise Intervention Trial on Allostatic Load in Black Women at Increased Risk for Breast Cancer: The FIERCE Study. *Journal of Racial and Ethnic Health Disparities*, 10.1007/s40615-021-01145–x. https://doi.org/10.1007/s40615-021-01145-x
- Arenillas, J. F., Moro, M. A., & Dávalos, A. (2007). The Metabolic Syndrome and Stroke:

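### Section 7.1 deletes all stored data on request without exception, which can erase adverse-event records and a randomised participant's allocation and outcomes

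*Protocol*

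**What the plan says.** Section 7.1 allows withdrawal at any time without a reason, and continues: "Upon request, all samples collected up to that point will be destroyed and all stored data will be deleted". No category of data is exempted there. The sections on informed consent (4.8), data management (6.2), monitoring (7) and adverse events (7.2) do not limit the rule either.

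Section 7.2 consists of one sentence: "Any unexpected or adverse events will be documented and promptly reported to the Ethics Committee".

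Section 6.3 states: "Statistical analyses will be performed in accordance with the intention-to-treat principles", and promises reporting to CONSORT with a flow chart. The design table in 3.3 also names intention-to-treat as the analysis.

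For identity protection the protocol has a separate device. Under 6.2 the password-protected master list "ensures that personal data can be deleted when the study is completed", and section 8 adds: "The master list, which combines ID and name, is deleted before the study data is published".

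**The concern.** A participant's wish to have data erased is legitimate. The difficulty is that 7.1 applies it to everything stored, including items the trial has promised to keep or use: the safety record, the assigned arm and the outcomes already measured.

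The trial is open-label, and controls are offered the programme only after T4. Harm from the hikes before T4 would therefore be expected mainly in the intervention arm. If people who were harmed or disappointed are more likely to ask for deletion, the loss is informative and favours the programme. That direction is plausible but not shown. Once the values are gone, no later analysis plan or sensitivity analysis can use them. The protocol and the consent form are therefore the place to settle the matter.

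**Working it through.** **Setting the rules side by side, for one participant who withdraws after T1 and asks for deletion**

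1. Section 6.1 lists randomisation at T-1, before the baseline examination at T1. This participant has therefore already been randomised.
2. Section 7.1 removes all stored data. On its plain wording this includes the adverse-event entry, the arm, the baseline and every later measurement.
3. Section 7.2 requires the event to be documented and reported. The report has gone to the Ethics Committee and survives there. The trial's own record, from which the publication would be written, does not.
4. Sections 3.3 and 6.3 require analysis as randomised. With no arm and no outcome, the participant cannot be analysed, and on the literal reading cannot be placed in the flow chart.

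**How many could be affected**

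Inputs: 70 per arm and 140 in total (4.6, 4.7); 40% assumed drop-out and loss to follow-up to day 180 (4.6).

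- Per arm: 0.40 × 70 = 28. In total: 0.40 × 140 = 56.
- This is a ceiling. It includes people lost to follow-up, who ask for nothing, and ordinary drop-outs, whose data are kept.
- The share who would ask for deletion is not in the protocol. Assumed shares of 5%, 10% and 25% of the 56 give 2.8, 5.6 and 14 people, or 2%, 4% and 10% of 140.

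**What this could do to SF-12**

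Let p be the fraction of an arm that is deleted, and D the mean change of those kept minus the mean change of those deleted. The mean of all is (1 − p) × kept + p × deleted, so the mean of those kept exceeds the mean of all by p × D.

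Assume that all requests come from the intervention arm, and that D is 2.5 to 5 points, the range of relevant change cited in 4.4.1. The trial's own threshold is 2.5 points.

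| Share of the 28 who ask (assumed) | People deleted | p = people / 70 | Shift, D = 2.5 | Shift, D = 5 | Percent of 2.5 points |
|---|---|---|---|---|---|
| 5% | 1.4 | 0.02 | 0.05 | 0.10 | 2–4% |
| 10% | 2.8 | 0.04 | 0.10 | 0.20 | 4–8% |
| 25% | 7 | 0.10 | 0.25 | 0.50 | 10–20% |

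The last row needs a quarter of all planned drop-outs in that arm to ask for erasure and none in the control arm. The shift is measured against the mean that would have included the deleted values, not against the true effect, so it illustrates scale only.

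**The case against.** The strongest counter-argument is that erasure on request is a deliberate protection, in a protocol that invokes the General Data Protection Regulation (4.8, 6.2). Whether coded data may be kept after such a request depends partly on the consent form and the project's data management plan, neither of which is in our copy. This stands as a reason not to abolish the offer. It does not explain why adverse-event records and study arm carry no exemption.

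A reader might also infer more than the documents support:

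- **Conflict with the audit-trail rule.** Section 7 says: "All entries and corrections are dated, documented and traceable or recoverable". In context this governs who may enter and correct data. It does not promise that no record is ever deleted at a participant's request.
- **Failure of last-value imputation.** It is true that nothing would be left to carry forward. But 6.3 confines that method to values missing at random, and deletion that depends on harm or disappointment falls outside it. The strain is on the general intention-to-treat commitment.
- **A large share of adverse events lost.** The protocol gives no expected event count, so no percentage can be supported. Events reported promptly also remain with the Ethics Committee.
- **A loss that could never be detected.** Individual values would be unrecoverable. Counts of randomised and analysed participants by arm need no individual data, and 7.1 does not say that such counts are erased.
- **A bias that must favour the programme.** Waiting-list controls may also leave and ask for deletion, which would offset the shift.

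**Conclusion.** The concern holds in a limited form. Section 7.1 states a rule that, followed literally, defeats the documentation duty in 7.2 within the trial's own records, and the intention-to-treat and flow-chart commitments in 3.3 and 6.3, for each participant who asks. This is a consequence of what the protocol fixes, not a detail left for a statistical analysis plan.

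The number affected is unknown and cannot exceed 28 per arm under the planned drop-out. The effect on SF-12 is probably small: 0.05 to 0.50 points under one-sided assumptions about who asks and how much worse they fared, none of which the protocol supplies. The firmer ground is the safety record, where each event matters and deletion is irreversible. The change is a cheap improvement; the point does not put the trial's main result in doubt.

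**What to change.** Amend 7.1, with a matching line in the informed consent (4.8), after the data protection officer has confirmed the wording:

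> On withdrawal no further data are collected. Coded data collected up to then are kept for the intention-to-treat analysis unless the participant requests their deletion. On request, samples, photos and locations are destroyed and coded outcome data are deleted; study arm, withdrawal date and adverse-event records are always kept in coded form. The master-list entry is deleted once any adverse-event follow-up and source-data check are complete. Deletion requests are reported by arm in the CONSORT flow chart.

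The master-list entry should not go at once. Cutting the link between code and person would block follow-up of an event and the source-data comparison planned in section 7.

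The amended wording applies to participants who consent after the amendment; those who consented under the present text keep its terms.

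The cost is one protocol passage, one consent amendment and a slightly narrower erasure offer. No visit, procedure or committee is added.

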7.2 Adverse events

Any unexpected or adverse events will be documented and promptly reported to the Ethics Committee.

8 Ethics and dissemination

Clinical trial results will be published in peer-reviewed journals and presented at scientific conferences. All publications and dissemination activities will respect the protection of personal data.

Publication rights are held by the parties involved in the study:

Lead partner:	Institute of Ecomedicine Paracelsus Medical University, Salzburg a.o. Univ. [name]. [name] and Team
Cooperation partner:	University Clinic for Internal Medicine I, with Gastro- enterology-Hepatology, Nephrology, Metabolism and Diabetology Salzburg University Hospital Prim. Univ. [name]. [name] and Team
RESONATE project partner	in accordance with the RESONATE Data Manage- ment Plan and the RESONATE Authorship Guide- lines RESONATE Lead Partner: Department of Cognition, Emotion, and Methods in Psychology University of Vienna [name], BSc MSc PhD and Team

Following FAIR Guiding Principles for scientific data management and stewardship, RESONATE will ensure that data generated and re-used throughout the project will be findable, accessible, interoperable, and reusable. As the primary repository, we will share and archive data on the Open Science Framework (https://osf.io/), which is a free and accessible platform.

To promote findability and implement our results within the wider nature-based solutions community, we will also share information and links to our results and datasets on OP-PLA (https://oppla.eu/), the EU repository for Nature-Based Solutions, to share and archive data. OPPLA is an open platform which can be accessed by people for different purposes, including non-scientific audiences. This will ensure that the results and benefits of the RESONATE project will also reach health care professionals, therapists, and municipalities. The master list, which combines ID and name, is deleted before the study data is published.

9 References

- Adams-Campbell, L. L., Taylor, T., Hicks, J., Lu, J., & Dash, C. (2021). The Effect of a 6-Month Exercise Intervention Trial on Allostatic Load in Black Women at Increased Risk for Breast Cancer: The FIERCE Study. *Journal of Racial and Ethnic Health Disparities*, 10.1007/s40615-021-01145–x. https://doi.org/10.1007/s40615-021-01145-x
- Arenillas, J. F., Moro, M. A., & Dávalos, A. (2007). The Metabolic Syndrome and Stroke:

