2.3 Nature-based Therapies und MetS

The Austrian Moderate Altitude Studies (AMAS) were the first nature-based interventions to address metabolic syndrome. AMAS I (2000) focused on the indicators of metabolic syndrome, which include overweight, disturbed blood sugar and blood fat metabolism, as well as elevated blood pressure. These factors pose significant cardiovascular risks. AMAS II (2006) focused on individuals with high stress levels. The studies have demonstrated that an active connection with nature, which involves a combination of hiking and active or passive regeneration, at moderate altitudes in the Alps (between 1,500 and 2,500 meters) under the guidance of professional coaches, has positive effects on individuals with metabolic syndrome, as well as on clients suffering from stress. These effects include a reduction in blood pressure and heart rate, an increase in the circulation of endothelial stem cells, and a reduction in body weight without the need for specific dietary measures. Additionally, there are positive psychological effects such as improved sleep quality, wellbeing, and social and physical recuperation (Gunga et al., 2003; Neumayr et al., 2014; Schobersberger et al., 2003, 2005, 2010).

Therefore, it can be inferred that nature-based interventions are a safe and effective method for reducing symptoms of metabolic syndrome and improving human health and well-being. However, it should be noted that the studies mentioned above were

conducted in a holiday setting. The proposed study, NATURE-MET-S, will concentrate on integrating nature-based therapies into daily life. This is a novel but promising approach to the secondary prevention of metabolic syndrome.

NATURE-MET-S aims to provide reliable evidence for indication-specific nature-based therapies. In the context of the HORIZON EUROPE project RESONATE¹,, it also aims to provide guidelines for the development and implementation of regionally based, resilience-promoting nature-based therapies in health care.

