4.3 Intervention

Nature-based therapy (NBT) consists of the components green exercise/hiking and nature-based mindfulness training.

The hikes are designed to accommodate individuals with varying levels of fitness. Each hike lasts between 1.5 and 2 hours. Participants will traverse distances between 3 and 6 kilometers and ascend to elevations of up to 300 meters on the Salzburg city mountains. A heart rate monitor (wristwatch) will be provided to each participant, which will be calibrated to their specific gender, age, height, and weight. This monitor will be used throughout the intervention. It is recommended that participants complete the hikes within the range of 60-70% of their maximum heart rate (Steele et al., 2021). Additionally, it is advised that training be conducted at a medium level of exertion on the Borg scale (12-16) (Borg, 1982; Löllgen, 2004). A guided group is limited to a maximum of 15 participants and is accompanied by a hiking guide and a mindfulness trainer.

Mindfulness training is based on concentrative movement therapy (Stolze & Badura-MacLean, 2002), a body psychotherapy method that combines physical movements and concentration to promote awareness and mindfulness of one's own body. The objectives of this form of mindfulness training are threefold: firstly, to enhance body awareness through targeted movement exercises; secondly, to reduce stress and promote general well-being; and thirdly, to cultivate mindfulness by training individuals to focus their attention on the present moment.

Intervention group (Nature group) :

Week 1 (day 0 - day 7): Onboarding

- a. 3 x 1,5-2h Green Exercise (guided hikes on the Salzburg city mountains,
 3-6 km each, 100-300 hm, max. 15 people per group)
- b. Within these hikes, participants will receive 20 minutes of nature-based mindfulness training under the guidance of a therapist in a pre-selected restorative and safe location. It is important to note that participants will learn mindfulness training during the process so that they can continue to practice it independently.
- c. It is required that all participants engage in the guided hikes during the initial week of the program.

Week 2 – Week 5 (day 8 – day 35): Integration

- a. 3 x 1,5-2h Green Exercise per week (guided or self-guided hikes (participants can choose) on the Salzburg city mountains, 3-6 km each, 100-300 hm)

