- b. During these hikes, participants will engage in 20 minutes of mindfulness training in a natural and safe environment.
- c. In weeks 2-5, participants may elect to embark on the hikes independently or to participate in the guided hikes.

Week 6 – Week 10 (day 36 – day 70): Self-guided

- a. 3 x 1,5-2h self-guided Green Exercise peer week (Hikes close to home according to prepared tour recommendations 3-6 km, 100-300hm)
- b. During these hikes, participants will engage in 20 minutes of mindfulness training in a natural and safe environment.
- c. In weeks 6-10, no further guided hikes will be offered; participants will be encouraged to conduct the sessions independently. During this period, participants will receive notifications to conduct the therapy sessions via the MyCap app. They will also be requested to complete the app-based questionnaire three times a week during the therapy sessions.

In weeks 11-26, participants will no longer receive reminders to complete therapy sessions. Similarly, they will no longer receive active requests to complete the app-based questionnaire.

The tour recommendations are located throughout Salzburg city to prevent repetition and promote self-determination.

The tour offers recommendations for hikes of varying difficulty levels. Following the initial guided hike, participants are classified according to their fitness level. This is achieved by measuring their heart rate during the hike using a heart rate monitor and by assessing their perceived exertion using the Borg scale (Löllgen, 2004).

The therapy sessions are documented at the location of the mindfulness training sessions using the smartphone app *MyCap*. MyCap is a free, mobile, REDCap-based application for study participants that can be installed on iOS and Android devices to collect the results reported by participants for a specific study previously created in REDCap. The integration of MyCap into REDCap provides a comprehensive and secure data collection system, which is particularly well-suited to longitudinal studies that require frequent requests for information from participants (Harris et al., 2022). The questionnaire asks about the current mood (SPANE, PRS), the perceived exertion, whether the therapy session is being conducted in a group or individually, and whether the patient used public transportation to get to the session (see also 4.4 Outcome parameters).

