A clinically relevant change in the Allostatic Load Index (ALI) is defined as a reduction in the ALI value that reflects a significant improvement in physiological markers associated with chronic stress and metabolic dysfunction. To be considered clinically relevant, a change should indicate a significant improvement in the above biomarkers, leading to improved overall health and reduced risk of metabolic and cardiovascular disease. In clinical trials, a reduction in ALI of approximately 0.5 to 1.0 standard deviations is often used as a threshold for clinical relevance. This range indicates a significant reduction in physiological stress, which can have a significant impact on overall health and the risk profile for complications associated with metabolic syndrome (Osei et al., 2022). In the present study, a reduction in ALI of 0.5 standard deviations or more is therefore defined as a clinically relevant change.

II. Primary endpoints – Perception of the intervention and short-term effects (t1-t4)

The evaluation of individual nature-based interventions is conducted using the MyCap mobile app (Harris et al., 2022). Participants are asked to complete the following questionnaires for each session:

- 1) Nature connection at the nature exposition site
- 2) Individual or group setting
- 3) Provide details on the mode of transportation used to reach the intervention site, such as public transport, car, or bicycle.
- 4) Perceived Exertion during physical activity via Borg Scale (Löllgen, 2004)
- 5) Surrounding photo (no identifiable persons!)
- 6) Affective states:
 - a. German version of the Scale of Positive and Negative Experience (SPANE) (Diener et al., 2009)
 - b. German short version of the Perceived Restorativeness Scale (PRS), (Pasini et al., 2014)
- 7) Ecologic aspects
 - a. Landscape
 - b. Environmental attitudes
 - c. Crowding
- 8) Overall satisfaction with NbT session

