6.1 Data collection

Data collection takes place at four time points: Day 1 (t1), day 35 (t2), day 70 (t3) and day 180 (see also chapter 4.5 Study timeline).

The data collection process at time points t1, t2 and t3 is almost identical. The data collection on day 180 is carried out as an online questionnaire survey. It should be noted that some data is collected only once, e.g: socio-demographics (t1), satisfaction with the intervention (t2).

As part of the initial examination (t1), all study participants will undergo a clinical assessment with the study physician on duty, who will decide whether or not the participant is eligible to participate in the study.

Data will be collected by qualified staff of the Institute of Ecomedicine at the Paracelsus Medical University and the University Clinic for Internal Medicine I at the University Hospital of Salzburg according to the following data collection plan:

- T-1 (as soon as there is a positive vote from the Ethics Committee): recruitment, randomization
- T1 resp. day 1: baseline examination
- T2 resp. day 35: examination after guided intervention
- T3 resp. day 70: follow-up examination 1
- T4 resp. day 180: follow-up examination 2

Digital data entry will be performed in a secure REDCap⁵ database system, which will be set up for the NATURE-MET-S study to securely store and process pseudonymized data. REDCap is a secure web application for building and managing online surveys and databases.

In addition, the participants will evaluate the individual therapy sessions using the Mycap mobile app⁶. The following data will be collected:

- Intervention location
- Date, time
- Connectedness to nature
- Individual or group setting
- Details of travel to the intervention location
- Self-assessed physical activity
- Photo of the surroudings (no persons!)
- Affective States (I-PANAS-SF, Perceived Restorativeness Scale (PRS))

MyCap is a freely available participant-facing mobile application that can be installed on iOS and Android devices to capture patient-reported outcomes for any REDCap project.

⁵ REDCap (project-redcap.org)

⁶ https://projectmycap.org/

MyCap's integration with REDCap provides a comprehensive data collection ecosystem and is best suited for longitudinal studies with frequent requests for information from participants (Harris et al., 2022).

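### Adverse events are to be promptly reported, but the protocol gives no method or period for asking about them, although 50–90% of scheduled hikes take place without study staff

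*Protocol*

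**What the plan says.** The whole adverse event provision is the sentence in section 7.2: "Any unexpected or adverse events will be documented and promptly reported to the Ethics Committee". It names no question, interval, observation period or responsible role, and does not say whether both arms are asked in the same way.

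Section 4.3 sets three hikes a week for ten weeks. In week 1 supervision is mandatory: "It is required that all participants engage in the guided hikes during the initial week of the program". In weeks 2–5 each participant chooses between guided and self-guided hikes. After that, "In weeks 6-10, no further guided hikes will be offered; participants will be encouraged to conduct the sessions independently". A guided group has a hiking guide and a mindfulness trainer with it.

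For the app, section 4.4.1 (part II) says "Participants are asked to complete the following questionnaires for each session" and then itemises the content; sections 4.3 and 6.1 give similar lists. App prompts stop after week 10.

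Both arms are examined on site at T1, T2 and T3 (days 1, 35 and 70). For T4, section 6.1 says "The data collection on day 180 is carried out as an online questionnaire survey".

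**The concern.** A promise to report promptly depends on someone learning of the event. The protocol lists in detail what is asked after each hike, including landscape, crowding and means of transport, but gives no item on injury, symptoms or medical contact.

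The population is sedentary, aged 40–65, with metabolic syndrome. The background in section 2.3 concludes: "Therefore, it can be inferred that nature-based interventions are a safe and effective method for reducing symptoms of metabolic syndrome". That inference rests on earlier hiking programmes led by professional coaches. The same section cautions that they took place in a holiday setting and calls integration into daily life novel. The self-guided phase is therefore where existing evidence helps least and where the trial's own event data matter most.

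Two things are at stake. Events on self-guided hikes may be learned of late or not at all. Any tabulation of events by arm may also partly reflect how much contact each arm had with the study team.

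**Working it through.** **Step 1. Hikes without study staff.** Inputs are from section 4.3, at 3 hikes per week.

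- Week 1, all guided: 3 × 1 = 3
- Weeks 2–5, guided or self-guided by choice: 3 × 4 = 12
- Weeks 6–10, all self-guided: 3 × 5 = 15
- Total: 3 + 12 + 15 = 30

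The minimum without staff is 15 of 30 = 50%. The maximum, if every optional hike is self-guided, is 15 + 12 = 27 of 30 = 90%. Hikes continued in weeks 11–26 are not counted.

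With 70 participants in the intervention arm (section 4.6), this is 70 × 15 = 1,050 to 70 × 27 = 1,890 sessions. Suppose the assumed 40% dropout leaves 42 participants and those who leave contribute no such sessions. The range is then 42 × 15 = 630 to 42 × 27 = 1,134.

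**Step 2. Search of the listed data for an event question.**

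| Source | Content | Event question listed? |
|---|---|---|
| App items (4.3, 4.4.1 II, 6.1) | nature connection, setting, transport, exertion, photo, mood, restorativeness, ecology, satisfaction | No |
| Endpoints t1–t3 (4.4.1, 4.4.2) | SF-12, allostatic load, vital signs, lung function, blood analysis | No |
| Questionnaires t1–t4 (4.4.2) | resilience, mindfulness, activity, nature contact, well-being, social aspects, motivation, environment, economics, process evaluation | No; care-service use is the nearest |
| Day-180 survey (6.1) | online questionnaire | None described |
| Internal audits (section 7) | site requirements, source data, sample storage | No event review |

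**Step 3. Possible delay.** The self-guided phase starts on day 36 and the next on-site visit is on day 70. An event early in that phase, if not volunteered, could wait up to 70 − 36 = 34 days before staff see the participant. From T3 to T4 the gap is 180 − 70 = 110 days, ending in an online form. That gap applies equally to both arms, so it bears on timeliness and not on imbalance.

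**Step 4. Contact by arm.** Examinations and the day-180 survey are scheduled alike in both arms. Guides and trainers (week 1, optionally weeks 2–5) and per-session app contact (prompted up to week 10) belong to the therapy, so the control arm does not have them during the trial. Passive capture depends on contact, and contact differs. The protocol gives no capture probabilities, so the size of any resulting bias cannot be calculated.

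**The case against.** The strongest reply is that absence from a list proves little. Adverse events are not endpoints here and would not be expected among them. Section 6.1 does not itemise the visit form, and the interview questions are in an appendix that is not shown. This stands in part: the app lists are the firmer evidence, because they set out what is collected per session. Those interviews take place after the intervention, however, and could not deliver prompt reporting. How participants are asked about events is protocol content, so a separate analysis plan would not close the gap.

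Care-service use at t1–t4 could bring medically attended events to light. That also stands. But it is listed for cost savings, with no event date, severity or causality stated, and is collected only at the four time points.

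Three stronger readings are tempting and are not supported:

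- *Events on self-guided hikes go unseen, and prompt reporting is impossible.* Participants may volunteer events, both arms meet staff at days 35 and 70, and promptness can reasonably run from when staff learn of an event.
- *The arms are ascertained unequally, as a fact.* This is an inference from differing contact. More contact could raise reporting in the intervention arm, but events on its self-guided hikes may also be missed.
- *Participants hike alone.* Self-guided means without study staff; the app itself records whether the session was individual or in a group.

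Finally, the protocol plans no safety endpoint and no test of events between arms. The bias matters only if such a comparison is later made.

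**Conclusion.** The point holds in limited form. Section 7.2 makes a promise for which the protocol states no method or period of elicitation, and none of the listed data items supplies one. Between 50% and 90% of scheduled sessions in the intervention arm lack study staff, and events there are captured only if volunteered or found incidentally. Passive capture is likely to differ between arms, with direction and size unsettled.

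This rests on two assumptions: that the lists reflect what is actually collected, and that the appendix and visit forms not shown contain no structured event question. If such a question exists, the remedy reduces to citing it in 7.2. The matter should be corrected, but it does not affect the validity of the primary efficacy comparisons.

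**What to change.** 1. At T2, T3 and in the T4 online form, ask both arms the same structured event question, covering the time since the last contact.
2. Add one yes/no event item with a details field to the MyCap session form, so that events on self-guided hikes reach the study team earlier.
3. State in 7.2 that events are collected from T1 to T4 in both arms by these questions, and that any comparison between arms uses only the common T2/T3/T4 answers. App reports, which only the intervention arm can give, are described separately.

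The cost is a short amendment, slightly longer forms in systems already in use, and some additional review of minor events by existing staff. No visit is added. If app entries were to trigger real-time alerts, monitoring effort would have to be planned; the change above does not depend on that.
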